### 4.4 Sample size calculation

In international literature there is scarce information about the percentages of treatment failure in patients admitted with an AECOPD receiving usual care. Therefore, we have performed a further search on PCT studies with a primary outcome of 30-day treatment failure. In the study by Schuetz et al. (JAMA 2009), who studied patients with lower respiratory tract infection, 30-day treatment failure was observed in 15.5% of the patients randomised to biomarker-based treatment, as compared to 18.9% in those randomised to usual care. This implies a relative risk of 0.82 in favour of the biomarker-based strategy. The study by Schuetz et al. was designed as a non-inferiority study, using a non-inferiority boundary of 7.5%. In view of these data we decided to design our study as a non-inferior study, whereas we choose a non-inferiority boundary of 5.0%. We based the primary outcome on the study of Huang et al. (NEJM 2018) (15). The incidence of the primary outcome was 20.4%. Using the relative risk of 0.82 in favour of the PCT-guided treatment group we expect the incidence of the primary outcome to be 16.7% in the PCT-guided treatment group. Then a total sample size of 626 is required (313 per treatment arm) to demonstrate non-inferiority with a power of 80%, and applying a one-sided alpha error of 0.025. We aim to enroll a total of 690 patients, accounting for a 10% drop-out rate. Because of an interim-analysis this number of patients will increase to 693 (as detailed below in section 10.4).

## 5. TREATMENT OF SUBJECTS

Patients will be randomized into:

- biomarker-guided treatment based on blood procalcitonin level to receive amoxicillin-clavulanic acid 875/125 mg three times a day for 5 days or no antibiotic treatment depending on the serum PCT-level

*or alternatively to*

- 
- usual care depending on the clinical decision of the physician to start or to withhold antibiotic treatment consisting of amoxicillin-clavulanic acid three times a day 875/125mg. The duration of treatment will also be by physician's choice.

*In case of a bêtalactam or penicillin allergy:*

- *doxycycline 100mg (200 mg on the first day) once daily for 5 days*

All patients will receive prednisolone 40mg once a day during 5 days, following the Dutch national guideline (16).

Next to antibiotics and prednisolone allocation as detailed above, all patients will additionally receive all standard care according to the Global Initiative for Chronic Obstructive Lung Disease (GOLD) 2018 guidelines and the Dutch guideline for care for patients with an acute exacerbation of COPD (16).

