### **10. STATISTICAL ANALYSIS**

There will be two analysis populations for this study:

1. The Intention-to-Treat (ITT) population is defined as all randomised patients who took at least one dose of study drug.
2. The Per-Protocol (PP) population is defined as a subset of ITT population constituted by those patients who: a) met all inclusion/exclusion criteria, b) attained a sufficient compliance to the treatment received, treatment with prednisolone and/or antibiotics, when prescribed on admission for at least 5 days, and c) did not present serious deviations from the protocol.

The analysis of all the efficacy variables will be performed on both the ITT and the PP populations in order to assess the robustness of the findings from the ITT population. All the demographic and baseline patients' characteristics and safety outcomes will be analysed using the ITT population.

All efficacy variables will be analysed for ITT and the PPS, and the PP population will be considered the primary population for assessing efficacy.

---

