## **13. STRUCTURED RISK ANALYSIS**

### **13.1 Potential issues of concern**

Patients in both groups will either receive amoxicillin-clavulanic acid 875/125mg three times a day during five days or no antibiotic therapy. Common expected adverse events are: diarrhoea and other gastro-intestinal complaints. Patients will receive diary cards, these diary cards will be reviewed at each visits for symptoms, adverse events and exacerbations. In case of an adverse event measures will be taken to treat the existing adverse event.

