6.1 General Study Design and Plan

- Study design: prospective, randomized-controlled trial. Patients will be randomized to biomarker-guided treatment (based on blood procalcitonin level) or to usual care. In the usual care arm, and in the biomarker guided-arm in case of high ($> 0.25\mu\text{g/L}$) procalcitonin, patients will receive amoxicillin-clavulanic acid.
- Type of Comparison: non-inferiority.
- Type of control(s): usual care
- Level and method of blinding (e.g. double-blind): The patient and the outcome assessor will be blinded for the allocated treatment strategy. Two independent physicians will be selected per center to be the outcome assessors. The patient will not be blinded for the treatment itself (prednisolone with or without antibiotic therapy).
- Method of treatment assignment: We will use a block-randomisation with randomly alternating blocks of 4 and 6 patients (random permuted block randomisation). The randomisation will be stratified per center.
- At what point in time subjects are randomized relative to treatments, events and study periods: Upon presentation at the emergency department, patients will be clinically

judged for in- and exclusion criteria, among which indication for hospitalization. When eligible the patient will be notified about the study. When the patient is interested in participating, the patient information form will be discussed by the treating physician. The participation being voluntarily and the opportunity to discontinue participation will be made clear by the treating physician. Informed consent will be requested with at least two hours of time to decide

- Sequence and duration of all study periods: screening will occur on the first day of admission as described above, baseline characteristics will be collected within 24 hours of admission, active treatment will be 5 days, follow-up will be 30 days.

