8.2.2 Per Protocol Population

- All subjects who:
 - met all inclusion/exclusion criteria,
 - attained a sufficient compliance to the treatment received, treatment with prednisolone and/or antibiotics, when prescribed on admission for at least 5 days,
 - did not present serious deviations from the protocol.

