9.3 Protocol Deviations

When a physician decides to prescribe antibiotic therapy even though the patient has a low serum concentration of procalcitonin ($\leq 0.25 \mu\text{g/mL}$) this leads to a protocol violation. The patient might recover because of the antibiotic therapy instead of still experiencing symptoms on day 30, which could directly impact the primary endpoint. This subject should not be analyzed in the per protocol analysis, because of this major protocol deviation/violation.

Early termination of antibiotic therapy, in both groups, could have an impact on the primary endpoint. This could happen when a patient has an initial quick recovery and gets discharged from the hospital without antibiotic therapy and then has a relapse. We do not expect this to happen more in one of the two treatment arms, although a high PCT might lead to less frequent discontinuation of the treatment when the patient is discharged in the first 5 days (the antibiotic therapy should be given during 5 days in both groups).

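### The documents disagree on usual-care antibiotic duration, so the per-protocol rule can drop usual-care patients who followed their allocated strategy

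*Protocol*

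**What the plan says.** **Duration of the antibiotic course.** Under Protocol section 5, PCT-arm patients are "to receive amoxicillin-clavulanic acid 875/125 mg three times a day for 5 days or no antibiotic treatment", according to the PCT level. For usual care, the physician decides whether to give antibiotics, and "The duration of treatment will also be by physician's choice". Protocol 13.1 does not separate the arms: "Patients in both groups will either receive amoxicillin-clavulanic acid 875/125mg three times a day during five days or no antibiotic therapy". SAP 9.3 says that "the antibiotic therapy should be given during 5 days in both groups". SAP 6.1 says that "active treatment will be 5 days", again without a split by arm.

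**Per-protocol compliance.** Protocol section 10 requires sufficient compliance with the treatment received, described as "treatment with prednisolone and/or antibiotics, when prescribed on admission for at least 5 days". SAP 8.2.2 repeats this wording. Neither makes an exception for usual care. Both documents name PP as the primary efficacy population, with ITT alongside it.

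**Deviations.** SAP 9.3 states one explicit PP exclusion: antibiotics given despite a low PCT. On short courses it says only that "Early termination of antibiotic therapy, in both groups, could have an impact on the primary endpoint". It does not say whether such patients leave the PP population.

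**The concern.** Whether a short course in usual care counts as non-compliance depends on which passage is followed. Under Protocol section 5, a physician who gives fewer than 5 days is using discretion that belongs to the usual-care strategy. Under Protocol 13.1 and SAP 9.3, the same patient falls short of a 5-day course expected in both groups. In the PCT arm section 5 allows no such discretion, so a short course there is a true deviation.

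One compliance rule would then remove deviators from one arm and strategy-adherent patients from the other. Early stopping happens after randomisation and is likely to be related to recovery, so randomisation does not protect a comparison selected on it. Stopping may also differ by arm. SAP 9.3 allows that a high PCT could make discontinuation less frequent, and Protocol section 3 withholds the PCT result in usual care. The non-inferiority conclusion rests on this population.

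**Working it through.** **1. The two readings of the PP criterion.** The clause is "when prescribed on admission for at least 5 days".

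| Usual-care course | Reading A: at least 5 days of treatment required | Reading B: test applies only to courses prescribed for 5 days or more |
|---|---|---|
| Planned from the start as shorter than 5 days | fails | not tested, stays in |
| Prescribed for 5 days, stopped early at the physician's discretion | fails | may fail |
| Longer than 5 days | passes | passes |

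The exposure is to short courses only. Reading B removes part of it, but not the courses stopped early.

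**2. The plan's own figure.** Inputs from Protocol 4.4: failure 20.4% in usual care and 16.7% in the PCT arm, margin 5 points, one-sided alpha 0.025, power 80%.

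n per arm = (1.960 + 0.842)² × (0.204×0.796 + 0.167×0.833) / (0.05 + 0.204 − 0.167)² = 7.849 × 0.3015 / 0.00757 = 312.6, so 313 per arm and 626 in total, as stated. At one-sided 0.0246 (half of the 0.0492 in Protocol 10.4) the result is 315 per arm, also as stated. The sample size is not in dispute.

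**3. Shift in the usual-care PP failure rate.** Let w be the share of the usual-care arm dropped and f the failure rate among those dropped.

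PP rate = (0.204 − w×f) / (1 − w)

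w = 0.65 × share of courses that are short. The 65% is the national figure in Protocol section 1, applied here to the usual-care arm. The documents give neither the short-course share nor f. Both are assumed.

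| Short courses | w | f = 10% | f = 15% | f = 30% |
|---|---|---|---|---|
| 10% | 0.065 | 21.12% (+0.72) | 20.78% (+0.38) | 19.73% (−0.67) |
| 30% | 0.195 | 22.92% (+2.52) | 21.71% (+1.31) | 18.07% (−2.33) |

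If the dropped patients fail at the arm average of 20.4%, there is no shift, only a loss of numbers. Usual care falls from 315 to 295 (10% short) or 254 (30% short), and power falls from 80.1% to 78.6% or 75.1%.

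**4. Effect on the error rate.** Take 20% short courses (w = 0.13), a true difference exactly at the margin (PCT-arm failure 25.4%), 315 patients in the PCT arm, and no PCT-arm exclusions. The chance of wrongly concluding non-inferiority is Φ((0.05 + PP rate − 0.254)/SE − 1.967), where SE is the unpooled standard error of the difference.

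- f = 10%: PP rate 21.95%, one-sided error 6.4%.
- f = 30%: PP rate 18.97%, one-sided error 0.9%.
- Planned: 2.46%.

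**5. Offset from the PCT arm.** Short courses there leave the PP population too. If 40% of that arm is treated, 30% of those courses are short and the dropped patients fail at 10% (all assumed), then w = 0.12. The PCT rate becomes (0.167 − 0.012)/0.88 = 17.6%, a rise of 0.9 points. The largest upward shift in the difference would fall from 2.5 to about 1.6 points.

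**The case against.** A reader might infer that the rule favours non-inferiority: short courses go to patients who recover quickly, and dropping those low-risk patients raises the usual-care failure rate. The documents do not support that. The case described in SAP 9.3 is a quick initial recovery, discharge without antibiotics, and then a relapse. Readmission is a component of the primary endpoint, so dropping such patients would lower the usual-care rate and count against the PCT arm.

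A reader might also take it as settled that the PP rule excludes every short course. It is not. Reading B spares courses planned as short, and SAP 9.3 attaches no exclusion to early termination. This narrows the problem but does not remove it, because the choice of reading decides who is in the primary population.

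Two further points have weight. SAP 9.3 does not expect early termination to be more frequent in one arm, and PCT-arm exclusions could offset part of the shift. All efficacy variables are also analysed by ITT, so a distortion could become visible. Both only mitigate: the expectation of balance is qualified in the same sentence of the SAP, and the ITT analysis is secondary.

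**Conclusion.** The contradiction on duration is explicit, and the PP criterion is ambiguous in a way that changes the primary population. Usual-care patients who followed Protocol section 5 can be excluded under reading A, and possibly under both readings if their course was stopped early.

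The direction of the bias cannot be determined from the documents. With 65% treated and 10% to 30% short courses, the usual-care PP rate shifts by about +0.4 to +2.5 points at an assumed 10% to 15% failure among those dropped, and by about −0.7 to −2.3 points at an assumed 30%. These figures are before any PCT-arm offset. The outer values are close to half the 5-point margin, but they are corners of an assumed range and not predictions. The point should be settled because the remedy is cheap and the rule governs the primary analysis.

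**What to change.** 1. Reconcile Protocol section 5, Protocol 13.1, SAP 6.1 and SAP 9.3 on the duration of antibiotics in each arm. This review takes no view on which duration is right.
2. Before unblinding, restate the PP compliance criterion in Protocol section 10, SAP 8.2.2 and SAP 9.3 as adherence to the allocated strategy as reconciled. State it separately for each arm, so that no patient is excluded for care that the allocated strategy permits.
3. In the same text, say how the criterion treats a course planned as short and a course stopped early, so that only one reading is possible.

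The cost is a change of wording in the protocol and SAP. Sample size and data collection are unaffected; antibiotic consumption is already recorded at every scheduled assessment.

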### **5.1 Investigational product/treatment**

Patients will receive amoxicillin-clavulanic acid or no antibiotic therapy

### **5.2 Use of co-intervention (if applicable)**

N.A.

### **5.3 Escape medication (if applicable)**

**5.3.1** N.A.

---

## **6. INVESTIGATIONAL PRODUCT**

### **6.1 Name and description of investigational product(s)**

N.A.

### **6.2 Summary of findings from non-clinical studies**

N.A.

### **6.3 Summary of findings from clinical studies**

N.A.

### **6.4 Summary of known and potential risks and benefits**

N.A.

### **6.5 Description and justification of route of administration and dosage**

N.A.

### **6.6 Dosages, dosage modifications and method of administration**

N.A.

### **6.7 Preparation and labelling of Investigational Medicinal Product**

N.A.

### **6.8 Drug accountability**

N.A.

---

## **7. NON-INVESTIGATIONAL PRODUCT**

### **7.1 Name and description of non-investigational product(s)**

Not applicable: it is standard of care in all guidelines to administer prednisolone and antibiotics in the majority of patients. Our drugs and dosing are within registration label and adhere to the Dutch guideline for in-hospital treatment of COPD exacerbations (16) (in line with GOLD 2018).

### **7.2 Summary of findings from non-clinical studies**

These are not presented here: it is standard of care in all guidelines to administer prednisolone and antibiotics in the majority of patients. Our drugs and dosing are within registration label and adhere to the Dutch guideline for in-hospital treatment of COPD exacerbations (16) (in line with GOLD 2018).

### **7.3 Summary of findings from clinical studies**

Appendix 1

### **7.4 Summary of known and potential risks and benefits**

Appendix 1

### **7.5 Description and justification of route of administration and dosage**

Appendix 1

### **7.6 Dosages, dosage modifications and method of administration**

Appendix 1

### **7.7 Preparation and labelling of Non Investigational Medicinal Product**

Appendix 1

### **7.8 Drug accountability**

N.A.

---

## 8. METHODS

### 8.1 Study parameters/endpoints

#### 8.1.1 Main study parameter/endpoint

The primary objective of this study is to show that at hospitalization for a severe exacerbation of COPD, PCT-guided treatment regarding antibiotic use is non-inferior to usual care consisting of prednisolone and or antibiotics, in terms of treatment failure at day 30 for patients hospitalized because of an acute exacerbation of COPD (AECOPD). Treatment failure is defined as disease-related mortality, need for endotracheal intubation or vasopressors, renal failure\*, lung abscess/empyema, development of pneumonia or rehospitalization within 30 days after inclusion.

\*renal failure is defined as Kidney Disease: Improving Global Outcomes (KDIGO) stage 3 – new renal replacement therapy, tripling of baseline creatinine, or serum creatinine  $\geq 350$   $\mu\text{mol/L}$ .

#### 8.1.2 Secondary study parameters/endpoints

The secondary objectives of this study are to assess the following secondary endpoints:-

The key secondary objective is:

- Treatment failure defined as an incomplete resolution of the clinical signs and symptoms associated with the AECOPD at day 30 after inclusion of the study (i.e not reaching the baseline condition prior to the AECOPD) scored using the modified Anthonisen criteria.

The other secondary objectives are:

- Change in Quality of Life on day 1, 10, and after 30 days using the COPD Assessment Test (CAT)
- Decision to start antibiotic therapy after an initial opposite decision (after 48 hours)
- Side effects (gastro-intestinal complaints, allergic reactions)
- Cumulative antibiotic consumption
- Cumulative prednisolone consumption
- Length of hospitalization
- Time to complete resolution of symptoms according to daily symptom diaries evaluating the modified Anthonisen criteria
- Re-exacerbation within 30 days
- PROM symptom score: EXACT – Respiratory symptoms scale (at admission, at day 10 and at day 30 after admission)
- Non-Invasive ventilation after 72 hours of admission

#### 8.1.3 Other study parameters (if applicable)

Demographics

Vital signs

Sputum for routine bacterial cultures

Serum sample for storage at -80 degrees Celsius

Sputum sample for storage at -80 degrees Celsius

Charlson Comorbidity Index

---

### Cost-effectiveness analysis (CEA):

- General considerations

Alongside the clinical trial, an economic evaluation will be performed conform the guidelines of the Health Care Institute Netherlands (17). This evaluation will be conducted from a societal and payer's perspective. When adopting the societal perspective, costs will include 30-day inpatient and outpatient (emergency room, specialist visits) hospital costs, primary care costs (visits to GP and nurse practitioner), medication costs, ambulance costs, productivity costs, informal care costs and travel costs.

- Cost analysis

The resource utilization underlying these costs will be obtained from a combination of sources, including case report forms, hospital administrative systems and a patient's self-reported questionnaire, which is based on an adapted version of the iMTA Medical Consumption Questionnaire (iMCQ) (18). When adopting the payer's perspective only the costs covered by the Health Insurance Act will be included. Unit costs will be based on reference prices obtained from the costing manual (19). In a sensitivity analysis we will adjust the unit cost of a hospital day to reflect ward-specific and hospitalization-day-specific costs instead of average costs based on all patients in a hospital. Productivity costs will be based on the Friction Cost method (20).

Savings in health care costs are expected to result from a reduction in antibiotics use, a reduced length of stay and a reduction in the incidence of side-effects from antibiotics. These savings will be compared to the additional costs of adopting the procalcitonin-guided treatment, including the costs of additional lab tests.

- Patient outcome analysis

The difference in total costs between the two groups will be related to the difference in the following outcomes: QALYs, treatment failures and CAT (COPD Assessment Test). This will result in the following incremental cost-effectiveness ratios (ICER): costs per QALY, costs per treatment failure avoided and costs per additional patient with at least one MCID improvement in CAT. The utilities to calculate QALYs will be measured with the EQ-5D-5L with and without the respiratory bolt-on (21). The ICER's will be estimated using a decision tree model that synthesizes the evidence collected during the clinical trial. The uncertainty around the ICER will be estimated in probabilistic sensitivity analysis, the results of which will be graphically shown in a CE-plane and Cost-Effectiveness Acceptability Curve.

### Budget impact analysis (BIA):

- General considerations

A budget impact model to estimate the impact of large-scale implementation of the intervention will be developed. This model will be a transparent cost calculator that includes nation-wide estimates of the size of the COPD population that is hospitalized for exacerbations, scenarios on the proportion and speed of uptake of the procalcitonin-guided AECOPD treatment, and changes in costs as a result of this.

o Cost analysis

These analyses will be conducted in accordance with the ISPOR and Dutch guidelines of ZONMW, for time horizons between 1 and 5 years (22, 23).

**8.2 Randomisation, blinding and treatment allocation**

Upon presentation at the emergency department, patients will be clinically judged for in- and exclusion criteria, among which indication for hospitalization. When eligible the patient will be notified about the study. When the patient is interested in participating, the patient information form will be discussed by the treating physician. The participation being voluntarily and the opportunity to discontinue participation will be made clear by the treating physician. Informed consent will be requested with at least two hours of time to decide. Randomisation will occur by a computer-based program. We will use a block-randomisation with randomly alternating blocks of 4 or 6 patients (random permuted block randomisation) and with stratification by center and with stratification by pre-treatment with antibiotics. The patient will not be blinded for the treatment received (prednisolone with or without antibiotic therapy) but the patient will be blinded for the treatment strategy (usual care or PCT-guided treatment). The participating centers will appoint two physicians that will be outcome assessors. The outcome assessors will be blinded for the treatment strategy.

